#### Research Aims

Aim 1: To examine the feasibility and acceptability of MERA training in a sample of 20 OEF/OIF/OND male Veterans who have not initiated a PTSD evidence-based psychotherapy.

Aim 2: To gather data on the effectiveness of MERA by measuring pre- to posttraining changes in impulsive aggression and emotion regulation skills.

Exploratory aim: To obtain data on whether MERA increases PTSD evidence-based psychotherapy initiation, engagement, and completion.

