- b) The Emotion Regulation Questionnaire (ERQ) is a 10-item self-report measure with 2 factors that assess specific emotion regulation strategies: cognitive reappraisal (changing the way one thinks about a situation) and expressive suppression (not expressing the emotion outwardly but feeling it internally). More effective emotion regulation is indicated by higher cognitive reappraisal scores and lower expressive suppression scores. Internal-consistency estimates (alpha) were .80 for the reappraisal factor and .73 for the suppression factor in a college-student sample, and both were greater than .75 in a Veteran sample. Scoring is based on how well the items describe the individual in the past week, from 1 (strongly disagree) to 7 (strongly agree).
- 7) Aggression.
  - a) The Impulsive Premeditated Aggression Scale (IPAS) is a 30-item self-report measure that assesses impulsive and premeditated aggression. In psychiatric outpatients, Cronbach's alphas were .82 and .77 for premeditated aggression and impulsive aggression, respectively. Scoring is based on how well each item describes an individual's aggressive acts, from 1 (strongly disagree) to 5 (strongly agree). To determine eligibility for the study, the measure will be scored in a categorical method by calculating the total percentage of positive items ("strongly agree" or "agree") for each aggression subscale and classifying the Veteran as either a primarily impulsive or premeditated aggressor, based on which subscale has the highest percentage of positive items. The summed dimensional score for the impulsive aggression subscale will be used to examine pre to posttraining differences in impulsive aggression.
  - b) The Overt Aggression Scale (OAS) is a 17-item self-report measure that assesses frequency of different aggression acts, including verbal and physical aggression against self, other, and objects. Intraclass correlation coefficients of reliability ranged from .89-.99 in 2 adult psychiatric samples. The measure will be adapted for the current study to indicate frequency of each aggressive act over the past week. Aggressive acts will be summed to create a total score.

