Session 1 – Introduction to emotions (anger, sadness, and joy). Emotion regulation skills training.	
 
Training rationale.
 
Discussion of Veterans' current emotion regulation difficulties.
 
Psychoeducation about 3 basic emotions (anger, sadness, joy).
 
Identify: Triggers, accompanying thoughts, and physiological reactions for anger, sadness, and joy.
 
Demonstrate and practice 2 skills: Progressive muscle relaxation and grounding.
 

Session 2 – Life's influence on emotions. Education on remaining emotions (disgust and fear). Emotion regulation skills training.	
 
Discussion of how childhood and military influenced emotion regulation strategies.
 
Psychoeducation about remaining basic emotions (disgust and fear).
 
Identify: Triggers, accompanying thoughts, and physiological reactions for disgust and fear.
 
Demonstrate and practice at least 2 skills: Remembering values, diaphragmatic breathing, and cognitive restructuring.
 

Session 3 – Using emotion regulation	
 
Brief introduction to PTSD treatments.
 
Psychoeducation as to what emotional experiences to expect and how to manage them during PTSD treatment.
 

during PTSD treatment.	
 
• Demonstrate and practice 3 skills: Ride the wave (mindfulness), increase positive emotions, and visualization.
 
• Writing an action plan for next treatment step.
 

------------------------	-------------------------------------------------------------------------------------------------------------------------------------------------------------------------------------------------------------------------------

Posttraining assessment. One month after the third MERA session, Veterans will be reassessed by the master's level independent evaluator who conducted the pretraining assessment with a similar assessment battery (see Assessment Schedule for exact measures) to detect any changes in PTSD, emotion regulation, and aggression (Aim 2). Veteran will also complete an exit interview that they can express their opinion of the training and any suggestions for improvement. Veterans' independent aggression raters will be asked to complete the OAS again via a phone call.

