#### Data Analysis/Statistics

This pilot study is largely descriptive to determine the feasibility and preliminary effectiveness of MERA. Due to the small sample size, all alpha levels will be set at 0.1 with the goal of maximizing the chance of detecting statistical differences.

Aim 1: Veteran verbal feedback, collected at the end of the third MERA session, will be examined to improve the acceptability of the training. Frequencies will be calculated on the number of Veterans who were referred, completed the screen, completed the pretraining assessment, met eligibility criteria, and attended all 3 emotion regulation training sessions.

Aim 2. Our second aim was to explore changes in aggression and emotion dysregulation from pre- to post-treatment among patients who completed MERA. Given study attrition and our desire to use as much data as possible, the statistical design for the primary analyses was an intent-to-treat, mixed effects regression model examining the main effect of time as the effect of substantive interest. Analyses were conducted using the generalized linear mixed models module in SPSS Version 24 using data from all sessions. Data transformations using appropriate link functions given the nature of the data (e.g., log transformation due to significant skewness in the OAS across all time points), where necessary, were conducted. Results were back translated into the original metric for ease of interpretation. Where appropriate, pairwise comparisons between time points were examined to determine which time points differed from one another. Effect sizes are reported to provide context for statistically significant results. Finally, percentages were provided for the frequency of veterans' engagement in an EBP after MERA (Exploratory Aim).

Exploratory Aim. Frequencies will be used to examine the number of PTSD evidence-based psychotherapy sessions to determine initiation, engagement, and completion rates following MERA.

ADVERTISEMENT: Bulletin Board

Exact language of Advertisement:

Male Veterans Who Served in Afghanistan or Iraq

Manage Emotions to Reduce Aggression

Do you have PTSD and struggle to manage aggression? We are researching a 3-session emotion-regulation training that is designed to help Veterans manage emotions and decrease aggression.

Study Involves:

- 3 treatment training sessions
- 2 assessment sessions

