If interested in learning how to decrease your aggression and also want to help other Veterans by evaluating the treatment, please call

[name] at [contact] [name], Principal Investigator

Offered by James A. Haley

Veterans Affairs Hospital.

Funded by the Department

of Veteran Affairs'

Consortium to Alleviate PTSD.

IRB# 23884

Payment:

Veterans will not be paid for taking part in the 3-session training. However, they will be compensated for the pre and post-training assessments. After completing the pre-training assessment, each Veteran will receive a \$30.00 by direct deposit to his bank account. If he is eligible for the study based on screening questions and complete the training, he will complete a post-treatment assessment and receive a \$30.00 by direct deposit after the assessment. If you do not have a bank account, you can be paid by check. That is a maximum of \$60.00 if both assessments are completed.

Veterans will receive a Form 1099 from the VA, which is required to process their payments. This form requires that study staff to use whole social security number instead of just the last 4 digits.

Costs: There are no costs associated with the study over and above the costs that would be incurred from standard care or services. For VA patients, there may be co-payment costs for some of the non-research procedures for which the VA may not pay even if these occur while you are participating in this research. Some veterans are required to pay co-payments for medical care and services provided by the VA. These co-payment requirements will continue to apply to medical care and services provided by the VA that are not part of this study and that you would receive as part of your regular medical care.

**5. Sample size:** We request to consent up to 60 participants to account for potential dropouts. We aim for a sample of 30 Veterans. The final goal is to have complete pre- and post-treatment data for 20 participants. Up to 25 participants may need to complete the post-treatment assessment in order not to slow recruitment at the end of the study.

**6. Study Population with Inclusion/Exclusion Criteria:** Veterans enrolled at the Tampa VA and who meet the following criteria will be recruited to the study:

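### Effect sizes are promised only alongside statistically significant results, and no confidence intervals are mentioned, although the size of change is the Aim 2 result of a descriptive pilot

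*Combined protocol and SAP*

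**What the plan says.** Under Data Analysis/Statistics, the study is introduced this way: "This pilot study is largely descriptive to determine the feasibility and preliminary effectiveness of MERA". The same section sets the significance level: "Due to the small sample size, all alpha levels will be set at 0.1 with the goal of maximizing the chance of detecting statistical differences". Whether tests are one- or two-sided is not stated.

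The Aim 2 paragraph there plans a mixed effects regression with time as the effect of interest. It transforms skewed data such as the OAS, converts results back to the original scale, and compares pairs of time points where appropriate. It then says: "Effect sizes are reported to provide context for statistically significant results". This is the only statement on reporting effect sizes, and the public text mentions no confidence interval or other measure of precision.

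The purpose is given under Research Aims, Aim 2: "To gather data on the effectiveness of MERA by measuring pre- to posttraining changes in impulsive aggression and emotion regulation skills". For the IPAS, the measures section adds: "The summed dimensional score for the impulsive aggression subscale will be used to examine pre to posttraining differences in impulsive aggression". Section 5 (Sample size) aims for a sample of 30, allows up to 25 posttraining assessments, and says: "The final goal is to have complete pre- and post-treatment data for 20 participants".

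**The concern.** In a descriptive, uncontrolled pilot, the estimated change and its precision are the result; the p-value is secondary. The effect-size sentence reverses this, because significance decides which outcomes carry an effect size. Read as written, an outcome with p ≥ 0.10 need carry neither an effect size nor an interval.

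Two things follow:

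- **Selection.** In a small sample only large observed changes reach significance. Effect sizes shown only for those outcomes are overstated on average unless the true change is large.
- **Missing precision.** Without an interval, a reader cannot tell a well-estimated moderate change from one compatible with almost no change. This holds for significant and non-significant outcomes alike.

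The investigators plan to publish, and the pretraining procedures refer to later studies and a grant. The reported effect sizes may therefore be used to plan that work.

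**Working it through.** The plan states no power, expected effect or SD, so there is no figure of its own to reproduce. The check asks how much a p < 0.10 filter would distort effect sizes at the planned sample sizes.

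**Inputs from the plan**
- Alpha 0.10 (Data Analysis/Statistics).
- Complete pre-post data for 20, with up to 25 posttraining assessments (section 5). The sample aimed for is 30, which would apply to pre-post outcomes only if everyone were reassessed.
- In the assessment schedule, DERS, IPAS, CAPS-5 and the independent-rater OAS are measured only before and after training, so for them the mixed model comes close to a paired comparison. The OAS and ERQ have five occasions.

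**Assumptions**
- Two-sided tests and normally distributed changes.
- True dz (mean change / SD of change) of 0.2, 0.3, 0.5 and 0.8.

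**Step 1: smallest significant effect.** Minimum |dz| = t(0.95, n−1)/√n.
- n = 20: 1.729/√20 = 0.387
- n = 25: 1.711/√25 = 0.342
- n = 30: 1.699/√30 = 0.310

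In units of the raw-score SD, multiply by √(2(1−r)), where r is the pre-post correlation. At n = 20 this gives 0.39 for r = 0.5, 0.30 for r = 0.7 and 0.17 for r = 0.9. So at n = 20 a true dz of 0.2 or 0.3 cannot be significant in the right direction without being overstated.

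**Step 2: average effect size among significant results.** Simulate paired samples, compute observed dz = mean change / SD of change, and keep those with |dz|·√n above the critical t (400,000 samples per cell). The chance of non-significance is exact, from the noncentral t with n−1 degrees of freedom and noncentrality dz·√n.

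| True dz | n = 20: mean significant \|dz\| (ratio to true) | n = 20: chance p ≥ 0.10 | n = 25: mean significant \|dz\| | n = 25: chance p ≥ 0.10 | n = 30: mean significant \|dz\| |
|---|---|---|---|---|---|
| 0.2 | 0.53 (2.7) | 78% | 0.48 | 75% | 0.44 |
| 0.3 | 0.56 (1.9) | 64% | 0.51 | 57% | 0.47 |
| 0.5 | 0.64 (1.3) | 31% | 0.60 | 22% | 0.57 |
| 0.8 | 0.85 (1.07) | 4% | 0.83 | 1% | 0.82 |

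**Step 3: the same without the filter.** Averaged over all results at n = 20, observed dz is 0.21, 0.31, 0.52 and 0.83. That is about 4% small-sample bias, so for small and moderate effects the inflation comes mainly from the filter.

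**Step 4: what an interval would show.** An observed dz of 0.5 at n = 20 gives t = 0.5·√20 = 2.24, which is significant. Inverting the noncentral t at its 5th and 95th percentiles gives a 90% interval of 0.10 to 0.88.

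**Step 5: outcomes with five occasions.** A simulation used all sessions, with 30 enrolled and 20 with posttraining data (4,000 runs, normal data, equal correlation 0.5, linear change). Mean significant |dz| was 0.47, 0.50, 0.60 and 0.82 for the four true values, or 2.4, 1.7, 1.2 and 1.02 times the truth. A separate check with the overall 4-degree-of-freedom time test at n = 20 gave about 2.2, 1.7 and 1.3 times for true 0.2, 0.3 and 0.5. Using all sessions reduces the inflation but does not remove it for small or moderate effects.

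**The case against.** The strongest reply is that the sentence does not say effect sizes are given only for significant results. It promises them there and is silent elsewhere. The same paragraph converts results back to the original scale without any significance condition, so raw changes may well be shown for every outcome. That narrows the point: what may be missing for non-significant outcomes is an effect size and an interval, not necessarily the change itself. But an estimate without an interval carries no precision, and silence is not a commitment.

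Second, the inflation figures depend on assumed true effects, and nothing in the plan says which applies. At a true dz of 0.8 the inflation is 7% at n = 20. This is right, and the conclusion has to be conditional. The missing interval does not depend on it.

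Third, the approximations are imperfect. The n = 30 figures lie outside the stated range for pre-post outcomes; without them the less favourable n = 20 and n = 25 figures remain. A normal-theory dz is a loose stand-in for a skewed, log-transformed OAS, so the OAS figures show direction and rough size only.

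Fourth, the independent-rater OAS has an unclear status. The schedule lists it with the eligibility and descriptive measures, and the pretraining text uses it to check the Veteran's report. It is nevertheless collected before and after training, and it is described within the posttraining assessment of Aim 2 change, so reporting its change is supportable.

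**Conclusion.** The concern holds. The plan's only commitment on effect sizes is tied to significance and comes without intervals, which does not fit its descriptive purpose.

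If effect sizes are shown only where p < 0.10, the expected overstatement at 20 pairs is about 1.3-fold for a true dz of 0.5, rising to 2.7-fold for 0.2. It is nearly absent at 0.8. About 64% of outcomes with a true dz of 0.3, and 31% with 0.5, would fall outside the commitment. These figures rest on two-sided testing, normal changes, a paired-t approximation and assumed true effects.

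This is a reporting weakness, not a flaw in design or model. It should be corrected because the correction costs so little.

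**What to change.** Replace the effect-size sentence with:

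> For every Aim 2 outcome (OAS, independent-rater OAS, IPAS impulsive subscale, DERS total, ERQ reappraisal, ERQ suppression) and for exploratory CAPS-5, we report the pre- to posttraining change, an effect size with its standardiser named (post/pre ratio for outcomes analysed on the log scale) and a 90% confidence interval, regardless of p-value.

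The plan should also say whether the independent-rater OAS is an Aim 2 outcome or only a check on self-report. Optionally, it could state whether pairwise time comparisons are run only after a significant overall time effect.

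Part of the Aim 2 text is in the past tense. If the analyses have already been run, present this as fuller reporting and do not call it pre-specified.

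The cost is one sentence and a seven-row table from models already planned. There are no new data or visits, and alpha can stay at 0.10. The one downside is that unimpressive or imprecise estimates become visible.

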  - c) Independent verification of aggressive acts – all Veterans will have an adult (18 years or older) live-in partner, family member, or roommate with whom he has in-person contact most days of the week verify aggression by independently answering the OAS, based on the Veteran's behavior. Independent verification of aggressive acts is an important feature of high quality aggression research, improving the quality of data without, in our experience, hindering recruitment. Impulsive aggressors may have impaired memory of the aggressive acts because of the intensity of rage, and they often confuse anger with aggression. Veterans may not think they are improving if they still experience anger, even if they are not acting aggressively. However, it is the decrease of aggression, not the elimination of anger, that is the goal of the training. The independent aggression rater will complete the OAS before and after their Veteran participants in MERA via a phone call with the study staff.
  - d) The Pre Index Event Aggression survey is an 8-item self report of aggressive acts prior to the PTSD index event. Currently, there is no available instrument to briefly and retrospectively gauge aggression in Veterans across the life span. This is a new instrument that is being piloted with this study. This is not an outcome measure.

- 8) Veterans' acceptability of the training will be measured by an exit interview during the post-training assessment. The 25-item exit interview has 6 open-ended questions that asks about the most and least useful parts of MERA and suggestions for improvement. The 8 skills taught in the training are listed, and Veterans answer whether they learned the skill, are using it, and if it is helpful. The remaining items are either yes/no or Likert-scale questions that ask about therapist characteristics and the overall program experience.

Pretraining assessment procedures. Veterans who are eligible based on the phone screen will be scheduled for an in-person, pretraining assessment. Prior to the assessment, research staff will explain the study to the Veteran and answer any questions. After providing informed consent, the Veteran will complete study measures (described above in Measures and Assessment Schedule).

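### Aim 2 is labelled intent-to-treat, but the plan describes a post-training assessment only for Veterans who complete MERA, so as written the post-training DERS, IPAS, rater OAS and CAPS-5 would come from completers

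*Combined protocol and SAP*

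**What the plan says.** All references are to the combined protocol and SAP.

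- **Data Analysis/Statistics, Aim 2.** The aim is to explore change "from pre- to post-treatment among patients who completed MERA". The next sentence reads "Given study attrition and our desire to use as much data as possible, the statistical design for the primary analyses was an intent-to-treat", and specifies a mixed effects regression with time as the effect of interest, using data from every session.
- **Payment (section 4).** "If he is eligible for the study based on screening questions and complete the training, he will complete a post-treatment assessment", for which he receives $30.
- **Posttraining assessment (section 4).** "One month after the third MERA session, Veterans will be reassessed". For the raters: "independent aggression raters will be asked to complete the OAS again via a phone call".
- **Assessment schedule (section 4).** DERS, IPAS, CAPS-5 and the independent-rater OAS are marked at pre-training and at post-training (one month after MERA) and at no other visit. Veteran-reported OAS and ERQ are also marked at all three sessions. DERS and Veteran OAS appear under primary outcomes. IPAS appears under inclusion criteria and sample description, but item 7a of the measures makes its impulsive subscale the scale for pre-to-post change in impulsive aggression. Item 5d calls CAPS-5 change exploratory.
- **Aim 1 analysis.** Counts include Veterans who "met eligibility criteria, and attended all 3 emotion regulation training sessions".
- **Section 5, Sample size.** Up to 60 consented, a sample of 30, complete pre and post data for 20, and up to 25 post-treatment assessments.

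**The concern.** The two Aim 2 sentences name different populations: those who completed MERA, and everyone who entered. The assessment rules follow the first and the label follows the second. A Veteran who stops before session 3 has no date from which to count the one-month visit, and the payment text does not reach him.

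For a measure taken only before and after training, a leaver's post-training value is then absent by design. A reader who sees the intent-to-treat label on DERS, a listed primary outcome, or on the IPAS impulsive subscale would take the result to describe all entrants. The Aim 1 counts would show how many Veterans left, but not how they changed.

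The protocol gives some reason to doubt that leavers resemble completers. Section 1 says that Veterans who feared their emotions were less likely to finish PTSD psychotherapy, and section 2 names PTSD severity as a predictor of dropout. Both statements concern PTSD psychotherapy, not MERA.

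**Working it through.** **No plan figure to reproduce.** The documents give no power calculation, effect size, SD or attrition rate. What can be checked is whether the mixed model recovers leavers' change on a pre/post-only measure.

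**Inputs, all assumed.** Completers improve by 0.50 SD; *m* is the share without post data; *L* is leavers' true improvement in SD; *B* is leavers' minus completers' baseline in SD (higher is worse); *rho* is the pre/post correlation. The shares 17% and 33% are 1 − 25/30 and 1 − 20/30 from section 5. That section does not say that the 30 are MERA starters, or that 20 to 25 is expected retention, so these shares are also only illustrative.

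**Step 1: what the model reports.** With post data in completers only, the likelihood estimate of the overall post mean is the completers' post mean plus rho × (baseline mean of all − baseline mean of completers), and that bracket equals m × B. Subtracting the overall baseline mean gives

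reported improvement ≈ 0.50 + (1 − rho) × m × B.

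*L* does not appear. With B = 0 the model reports 0.50 SD whatever leavers did. With m = 1/3, rho = 0.5 and B = +0.5 it reports about 0.50 + 0.5 × 0.333 × 0.5 = 0.58 SD; with B = −0.5, about 0.42 SD. So leavers' baselines move the estimate, but their outcomes cannot.

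Fitting a random-intercept model to data built with exact means, variances and correlation (m = 0.167 and 0.333; rho = 0.3, 0.5, 0.7; B = 0, +0.5, −0.5) agreed with the formula within 0.002 SD.

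**Step 2: the true all-starter improvement** is (1 − m) × 0.50 + m × L:

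| Share without post data | L = 0 | L = 0.25 | L = 0.50 | L = 0.75 |
|---|---|---|---|---|
| 10% | 0.45 | 0.48 | 0.50 | 0.53 |
| 17% | 0.42 | 0.46 | 0.50 | 0.54 |
| 20% | 0.40 | 0.45 | 0.50 | 0.55 |
| 33% | 0.33 | 0.42 | 0.50 | 0.58 |

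For example, at 33% and L = 0: 0.667 × 0.50 + 0.333 × 0 = 0.33. At 33% and L = 0.75: 0.333 + 0.25 = 0.58.

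**Step 3: compare.** With equal baselines the model reports 0.50 in every cell. It is too large where L is below 0.50, right where L equals 0.50, and too small where L is above it.

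**Step 4: what assessing leavers would do.** With n = 30, rho = 0.5 and equal baselines, the model gives 0.500 when 5 or 10 leavers are not assessed. If the same leavers are assessed and show no change, it gives 0.417 (5 leavers) or 0.333 (10 leavers). The post-training visit is what supplies the missing information; the choice of model does not.

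**The case against.** The strongest reply is that silence is being read as a rule. The sentence that conditions the assessment on completion sits in lay payment text, while the procedure itself only sets a time and says that Veterans are reassessed. The measures section ties the rater call to participation, not completion: "The independent aggression rater will complete the OAS before and after their Veteran participants in MERA via a phone call with the study staff". This stands to the extent that a reader might infer that leavers are barred from assessment, or were in fact not assessed. The documents show neither. What remains is that the payment text, the timing and the Aim 2 wording agree with one another, and nothing describes a visit for a leaver.

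Three other strong readings also fail.

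- *Leavers are dropped from the analysis.* They are not. Their baselines enter the mixed model, which the plan chose with attrition in mind. A likelihood-based mixed model normally assumes missing at random; the plan does not say so.
- *The effect is overstated.* It may be overstated, correct or understated, as the table shows.
- *All of Aim 2 is affected.* Veteran-reported OAS, the listed primary aggression outcome, and ERQ are also taken at each session, so a leaver who attended any session contributes more than a baseline. They are less affected, though a leaver's one-month value is still unobserved.

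It is also fair that this is an uncontrolled, mainly descriptive pilot whose first aim is feasibility. But it tests at alpha 0.1, reports effect sizes and plans publication, so the population that a primary-outcome result describes should be stated correctly. Whether Veterans who attend no session belong in the analysis is a choice of estimand, and the plan may settle it either way.

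**Conclusion.** The point holds as an inconsistency between label, stated population and assessment rule, and should be fixed. Followed as written, the plan yields post-training DERS, IPAS, rater OAS and CAPS-5 data from completers only. The estimated change in these measures then stands for all entrants only if leavers' missing values are missing at random, which is not stated and which the scheduled data cannot test.

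Neither the size nor the direction of any bias can be derived from the documents. Under the assumed inputs with equal baselines, the gap between the reported 0.50 SD and the all-starter value runs from 0.17 SD too large (33% missing, leavers unchanged) through zero (leavers improve as completers do) to 0.08 SD too small (33% missing, leavers improve by 0.75 SD).

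If leavers were in fact assessed, saying so with counts would resolve most of the point. The two Aim 2 sentences would still need to be reconciled.

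**What to change.** **If data collection is open.**

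1. Amend the Posttraining assessment and Payment paragraphs so that every Veteran who starts MERA is invited to the post-training assessment and the rater call, with the $30 payment, one month after his planned third-session date whatever his attendance. Check the allowance of 25 assessments in section 5 against this.
2. Define the intent-to-treat set explicitly, including whether eligible Veterans who attend no session belong to it.
3. In Aim 2, remove the restriction to completers from the primary analysis and keep completers as a secondary analysis.

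Cost: a short amendment, then $30, one visit with the existing evaluator and one rater call per leaver who accepts (the documents do not give the number). The estimated effect may be smaller.

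**If data collection is over**, as the past tense of the Aim 2 text suggests.

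1. Report, for each measure, the number with pre and with post data, split by completers and leavers.
2. Only if no leaver gave post data, do not call the DERS, IPAS, rater OAS or CAPS-5 results intent-to-treat, and describe their post data as completer-only.
3. State the missing-at-random assumption.
4. Add a sensitivity analysis over a range of leaver change that includes no change and both smaller and larger improvement than completers.

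Cost: wording, a table of denominators and one sensitivity analysis, with no new data.
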